# 10.3.2.10 West Hertfordshire Hospitals NHS Trust

Patients using services at West Hertfordshire Hospitals can learn about how their data is used by the Trust by reading the local privacy notice. This notice includes statements that patient data might be used for research. There is also signposting to the NHS England and NHS Digital websites for more information. Patients are also told about their rights around use of their data and signposted to speak to their clinician if they object to their data being used in particular ways or if they wish to withdraw consent. This document confirms that there is a patient notification process in place about data use for research, as well as the ability to ensure that only unrestricted data will be included within reports for recruitment.

# 10.3.2.11 Whittington Health NHS Trust

The Trust's privacy notice includes information about how patient data may be used for research, as well as signposting patients to the national opt-out scheme (section 10.3.1) if they wish to restrict the use of their data. This notice confirms that there is a patient notification in place, as well as confirmation that patients at this Trust have been made aware of data use opt-out mechanism. Thus, any reports run by this site will be able to exclude patients who have stated that they do not want their information used for research.

#### 10.3.3 Legal Use of Email Addresses

In addition to NHS and local organisational policies, this approach has been made possible through section 251 of the National Health Service Act 2006, supported by the data collected through the PPI activity reported in this protocol's section 11. This is important to note as many of the above policies highlight that there are justifications to access being granted to researchers prior to consent. Additionally, this project is deemed as having benefit to public interest, both in definition and in the public's opinion (as discussed in PPI activities in section 5).

#### 10.3.4 Confidential Advisory Group Precedent Set Categories

The proposed method of recruitment also falls under the Precedent Category 1 of the Confidential Advisory Group pathways. The categories denote when a scenario requiring CAG oversight is considered to be "commonly-arising". This precedent is used is used for participant identification, allowing for access to data "on potential participants in order to send them study invitations or surveys."

#### **10.4** Recruitment and Notification Methods

In order to recruit patients that are actively receiving antenatal care, patient records will be accessed for patient names, gestational due dates, and email addresses. Development of these recruitment methods have been done in consultation with the site PIs and the supervisory team, with further advice provided through the patient and public involvement activities discussed earlier (Section 5). The following details the pathways and steps for recruitment. Methods for notifying patients about the study will include two pathways: contact via email with a screener questionnaire and notification done by the care team, in compliance with section 251.

#### 10.4.1 Pathway One: Recruitment via Email

The first pathway to recruitment is via email. This will take place by the study coordinator emailing current antenatal patients to inform them of the study and to invite them to complete the screener questionnaire.

To access the necessary email addresses, a report will be run each month by each site's contact person (i.e., research or IT midwife) to provide the eligible email addresses to be contacted. This list, in the form of a report, will be composed of active antenatal patients prior to 36 weeks gestation. Only patients whose data can used for research will be included within these monthly reposts (as explained in 10.3.2). Once generated, the reports will be securely uploaded to data safe haven where it will only be accessed by the study team. When patients are emailed an invitation to the study screener it will be sent to them via REDCap, the survey platform on the data safe haven. These emails will be sent out in small batches to use the minimal number of patients' emails each month, as discussed in the email protocol in appendix 3.

Along with a link to the screening questionnaire, the email provides information on how to remove themselves from the study contact list and how to opt-out of their information being used for research without their consent.

#### 10.4.1.1 Dissent Mechanism

In the case that there is no participation or reply, a dissent mechanism is in place to keep emails to patients minimal. After a potential participant has been emailed twice, with no response or engagement, they will be marked as "no further contact". A list of excluded emails will be kept in a secure file on the data safe haven. This list will be kept until the end of the study, to make sure that they are excluded from further contact in the case of another pregnancy during the recruitment window.

#### 10.4.2 Pathway Two: Notification methods

A concurrent, and secondary, pathway will be done by clinical staff as capacity allows. In part, this pathway is to address the need for additional notification methods to allow for there to be an alternative to the study team using email addresses if and when it becomes feasible at each location. To clarify, this is a list of the materials that will be made available to study sites, how sites use them may vary (i.e., over the phone bookings vs. face-to-face discussions, etc.). In addition to what is listed here, there may be routine recruitment approaches sites use to share information about ongoing studies with service users (i.e., active study lists, text alerts, notification during appointments, etc.). The following materials have been created and compiled to support recruitment and will be made available to all sites involved within the study to serve as these notification materials.

# 10.4.2.1 In-clinic Materials

A packet of materials has been put together that will be shared as digital files which can readily be printed on-site as they are needed (see appendices 7-10). The list of materials necessary to create has been generated based on the consultations held with the site PIs and the midwifery team members. The materials below are meant to support and not limit the methods the care team may choose to use for recruitment (when there is capacity). These study-related materials include:

- A tri-fold pamphlet for parents and providers with a QR code linking to the online PIS
- An A4 poster for being posted in-clinic with QR code
- A provider script for introducing the study to patients
- A contact slip to be used for both permissions to contact for recruitment and opting-out

# 10.4.2.2 Social Media Marketing Materials

Social media posts have been created for Twitter, Facebook, and Instagram (appendix 11) after consulting with the hospital sites. Full-size images will be provided to each site, with a preview of the images shared here.

# 10.4.2.2.1 Image Captions

This caption will be used across all the social media platforms:

# Pregnant?

We are recruiting LGBTQ+ and heterosexual pregnant patients for a student study on pregnancy and birth outcomes. If you are interested in participating in the study you can ask your care team for more information. Check out the study website at https://www.homepages.ucl.ac.uk/~stnvkll/

In addition to these social media posts, this study is using email addresses from patient records to recruit participants. To keep your email from being used, you can notify the study team that you do not wish to be emailed by filling out the opt out form at tinyurl.com/yck6twfu or by calling [contact].

10.4.2.2.2 Twitter Images

# Pregnant?

We are recruiting LGBTQIA+ and heterosexual pregnant patients for a study on pregnancy & birth.

If interested, ask your care team for more info and check out the study website: https://www.homepages.ucl.ac.uk/~stnvkll/

Site Logo Placeholder

Legacies and Futures, Twitter Image 1, IRAS: 264198, Version 1.2 (01/02/2022), REC References (21/LO/0551), CAG (21/CAG/0149)

L+F Twitter 1.jpg

L+F Twitter 2 v1-2.jpg

L+F Twitter 3 v1-2.jpg

10.4.2.2.3 Facebook Images

**Pregnant?** 

We are recruiting LGBTQIA+ and heterosexual pregnant patients for a study on pregnancy & birth.

If interested, ask your care team for more info and check out the study website: https://www.homepages.ucl.ac.uk/~stnvkll/

Legacies and Futures, Facebook Image 1, IRAS: 264198, Version 1.2 (01/02/2022), REC References (21/LO/0551), CAG (21/CAG/0149)

L+F Facebook 2 v1-2.jpg

L+F Facebook 1 v1-2.jpg

L+F Facebook 3 v1-2.jpg

#### 10.4.2.2.4 Instagram Images

# Pregnant?

We are recruiting LGBTQIA+ and heterosexual pregnant patients for a study on pregnancy & birth.

If interested, ask your care team for more info and check out the study website: https://www.homepages.ucl.ac.uk/~stnvkll/

Legacies and Futures, Instagram Image 1, IRAS: 264198, Version 1.2 (01/02/2022), REC References (21/LO/0551), CAG (21/CAG/0149)

L+F Instagram 1 v1-2.jpg

Site Logo Placeholder

Pre

LEGAC

& FUTURES STUDENT STUDY

L+F Instagram 3 v1-2.jpg

#### 10.4.2.2.5 Notification of CAG approval and opt out process

# **10.5** Participation Compensation

Funding have been received from the Society for the Psychological Study of Social Issues to cover the compensation of participants that are taking part in the sub-study (section 13). Participants will not be made aware of this compensation until after they have completed the activities.

# **11 CONSENT**

There are multiple steps in this study which will include phasing both prior to and after participant consent has been given. Appendix 12 provides a copy of the study consent form.

# **11.1** Activities Prior to Participant Consent

As part of the recruitment process, to be discussed next, there will be the need to contact current antenatal patients using their listed email addresses. Because this would take place prior to consent, the process will be conducted under Section 251 of the National Health Service Act 2006, which allows for access to patient data without consent for recruitment purposes. More detail is provided under section 8.1 of the protocol, including dissent and the reduction of contacting patients prior to their consent.

# **11.2 Participant Consenting Process**

Consent will be gathered through Research Electronic Data Capture (REDCap), a survey platform that is integrated into secure systems, hosted on the UCL Data Safe Haven. Collection of consent through electronic means has a supported precedence in medical studies in the United Kingdom^40 and abroad. Individuals interested in participating will be asked to consent to their participation in the study when they access a link to the REDCap survey. Using branching or digital skip logic, which limits the ability of user to proceed through a survey, the survey will require participants to acknowledge they have read the patient information sheet and are aware of what study activities they are consenting to through completing the form. This will allow for digital records of consent, with electronic time stamps, to be kept securely on the Data Safe Haven and to be archived separately from the study data upon completion. Besides checking boxes in agreement, participants will also type out their name and provide an electronic signature. Additionally, a copy of the participant's consent form will be immediately emailed to them for their records, so that they are able to refer back to the form if needed. More information on both REDCap and the Data Safe Haven is available in appendices 13 and 14, and are discussed within the data management plan below.

# **11.3** Time Limitations for Consent/Dissent

With the survey available online, the only potential limit to time for deciding is the length of their pregnancy. If participants have given consent and chose to no longer to participant and/or grant access, they can leave the study prior to any identifiable information being removed from the dataset (also called data pseudonymisation), with confirmation that their data will not be included within the dataset for final analysis.

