# 8.3 Identifying and Recruiting Potential Participants

At each site, a monthly report will be run by the PI or a supporting IT midwife. This report includes the relevant information of active antenatal patients with a gestational age higher than 16 weeks and lower than 36 weeks (i.e., with at least one month before their due date). Patients who have opted out of contact locally and nationally will be removed automatically as part of the search criteria. From this list, a selection of participants will be emailed by the researchers to be invited to take part in the study (see appendix 3 for selection process), this will be discussed in more detail in the section on recruitment below (see section 10). If interested, participants will follow a link in the email to a screener questionnaire (appendix 4) that will be used to assess eligibility. If patients screen eligible based on their responses to the screener, they will be emailed with an invitation to participate in the study and sent a link to provide consent and complete the study surveys.

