# 9.1 Inclusion Criteria

Patients must meet all of the following in order to be eligible for the study:

- Legal adult of reproductive age (18-49)
- Identifies as a lesbian, gay, bisexual, queer, nonbinary, intersex, and/or transgender (or cisgender and heterosexual for comparison sample)
- Currently pregnant and receiving antenatal care at one of the 4 study sites

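### The 16 to 36 week limit governs only the email report, so Survey 1 can be completed up to birth, including at gestations when a preterm birth can no longer occur

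*Protocol*

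**What the plan says.** - **Section 8.3** defines the monthly report as "active antenatal patients with a gestational age higher than 16 weeks and lower than 36 weeks" and explains the upper limit as "with at least one month before their due date". It also says that eligible patients get one link for both consent and the surveys.
- **Section 10.4.1** describes the same report as "active antenatal patients prior to 36 weeks gestation" and gives no lower limit.
- **Section 9.1** asks only that a person be "Currently pregnant and receiving antenatal care" at a study site. **Section 9.2** excludes people under 18 and people who use the site only for non-antenatal services. Neither mentions gestation.
- **Section 10.4.2** adds another route: "A concurrent, and secondary, pathway will be done by clinical staff as capacity allows". It covers pamphlets, posters, a staff script, a contact slip and social media, and states no gestational limit.
- **Section 11.3** says of consent that "the only potential limit to time for deciding is the length of their pregnancy".
- **Section 12.1** places Survey 1 in pregnancy without a week range. **Section 12.3.1.1** collects gestational length among the birth measures.
- **Section 8.4** matches controls to cases on due date, trust and planned place of birth. At least twelve patients are contacted for each LGBTQIA+ participant already confirmed.

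**The concern.** The upper limit in section 8.3 has a clear purpose, to leave time before birth, but it acts on the day the report is run and not on the day Survey 1 is completed. Several steps follow the report: batched emails, a second email, the screener, the invitation and consent. No stated rule rechecks gestation at any of them. People who arrive through pathway two never pass the report filter.

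The overview in section 1 names preterm birth among the complications of interest, and section 4.3 puts birth outcomes in the primary aim. A person who enters at week g can contribute only a birth after week g, so early births are selectively missing. From 37 weeks on, a preterm birth is impossible. If entry times differ between the groups, the missing early births differ too, and a comparison of gestational length or preterm birth would carry a bias unrelated to vulnerability or resilience.

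**Working it through.** **1. Which rule limits what.**

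| Step | Gestational limit stated |
|---|---|
| Email report (8.3) | above 16, below 36 weeks |
| Email report (10.4.1) | below 36 weeks |
| Inclusion and exclusion (9.1, 9.2) | none |
| Pathway two (10.4.2) | none |
| Consent (11.3) | end of pregnancy |
| Survey 1 (12.1) | end of pregnancy |

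Taking term as 40 weeks, 40 − 36 = 4 weeks, which agrees with the one-month reason in section 8.3. Consent and the survey share one link, so an open consent period means an open Survey 1 period. A patient listed at 35 weeks may, on the text, complete Survey 1 at 39 weeks.

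**2. Size in the email pathway.** The protocol gives no figure to reproduce, so this is an illustration on three assumptions:
- gestation on the report G is uniform over 16 to 36 weeks;
- the delay D from report to Survey 1 is uniform from 0 to 4.35 weeks (one month) or 0 to 8.7 weeks (two months), and independent of G;
- preterm means before 37 weeks. The protocol does not define it.

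With d the longest delay:
- P(G + D ≥ 37) = (d − 1)² / (2 × 20 × d)
  - d = 4.35: 3.35² / 174 = 0.065
  - d = 8.7: 7.7² / 348 = 0.170
- P(G + D ≥ 36) = d / 40
  - d = 4.35: 0.109
  - d = 8.7: 0.218

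For these delays the figures are upper ones, because some people would deliver before answering. Those people are lost to the sample, which is itself the truncation. For pathway two the documents give nothing from which to calculate.

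**3. Direction between groups.** Take a case and a control with the same due date. If the control is contacted after the case is confirmed, the control's gestation at contact is later. Matching fixes the due date but not gestation at Survey 1.

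**4. What a difference could do.** Let p be the true preterm rate in both groups and f the share surveyed at 37 weeks or later. Ignoring truncation below 37 weeks, the observed rate is p(1 − f), so the apparent risk ratio is (1 − f_cases) / (1 − f_controls), whatever p is. If cases had the one-month delay and controls the two-month delay, it would be 0.935 / 0.830 = 1.13 with no true difference. This shows the mechanism and is not an estimate.

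**The case against.** The passages govern different steps. A reader might infer that four rules contradict each other, but a report filter narrower than the eligibility criteria, with an unhurried time to decide, is not a contradiction. The one textual mismatch is the missing lower limit in section 10.4.1. What stands is that no stated rule carries the upper limit through to Survey 1.

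The screener (appendix 4) and the email protocol (appendix 3) are not shown and might check gestation. But section 8.3 uses the screener to assess eligibility, and the stated criteria contain no gestational rule for it to apply.

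The outcome can be overstated. A reader might infer that birth outcomes in general are settled for late entrants. Birth weight, length, head circumference and Apgar score can still vary after 37 weeks, and no binary preterm endpoint is fixed. Many survey scales describe standing circumstances or history, and the biomarkers come from records across pregnancy. A reader might also infer that the two surveys could fall days apart. The protocol gives no date for Survey 2, and a journal that runs into the first month after birth suggests a longer gap. The point is therefore confined to gestational length and any preterm comparison.

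The figures rest wholly on assumed distributions. After the first report, newly listed patients will mostly have just passed 16 weeks, which would lower the shares. Much larger false risk ratios can be produced: with 10% late entry in cases and 30% to 50% in controls, 0.9/0.7 = 1.29 to 0.9/0.5 = 1.80. Nothing in the documents supports late shares that high.

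Finally, delayed entry could be handled in a statistical analysis plan that is not shown. That would deal with the analysis but would leave the protocol's entry rules open.

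**Conclusion.** The point holds in a limited form. On the text of the protocol, the upper gestational limit is a search filter for one recruitment route, and Survey 1 can be completed at any time up to birth. Gestational length is left-truncated as a result. People surveyed at 37 weeks or later, under the assumed threshold, carry no risk of preterm birth. Because controls are contacted after their case is confirmed and are matched on due date, the truncation may differ between groups, with controls tending to enter later. That would make early birth look more common in cases.

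The size cannot be known from the protocol. About 6% (one-month delay) or 17% (two-month delay) of email-pathway participants would reach 37 weeks before Survey 1, on the assumed uniform distributions and as upper figures for those delays. Entry before 16 weeks is not part of this problem, because such participants are still at risk of preterm birth. The correction is cheap and should be made.

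**What to change.** 1. State one entry window in section 9.1 that keeps the existing upper limit. Check it from the due date when Survey 1 is completed, for both pathways. Decide whether the 16-week lower limit is meant, and make sections 8.3, 10.4.1 and 11.3 agree.
2. Derive gestation at Survey 1 from the due date and the REDCap time stamp, and account for it in the gestational-length analysis by delayed entry or adjustment. This remains necessary with the window in place, because entry times below the limit still differ.
3. Leave participants surveyed at 37 weeks or later out of any preterm-birth comparison, and out of that comparison only. Early entrants stay in.

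**Cost.** No new data are needed, since the due date is already used for matching and REDCap already time-stamps consent. Some late volunteers, including some from the scarce case group, are turned away or do not contribute to that one outcome. On the assumptions above, 11% or 22% of email-pathway participants would pass 36 weeks before Survey 1, again as upper figures. The plan's own recruitment figures leave room for this: 15% of 2,270 is about 340 LGBTQIA+ participants in 12 months, and 340.5 × (1 − 0.218) is about 266, against a target of 200. That margin depends on the planned 15% participation rate being reached. Prompt reminders to those nearest the limit would reduce the loss.

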  - Complications (i.e., further monitoring, need for time in NICU, miscarriage/stillbirth/infant mortality, etc.)
  - $\circ$  Care processes (i.e., skin-to-skin time, supplementation, etc.)
  - $\circ$  Any further tests requested by the care team related to infant health

Data transfer between the hospital sites and the data processors will take place over the secure network provided by the Data Safe Haven, hosted by UCL. The Data Safe Haven is a remote server that uses a wall-garden approach to allow for the securing of identifiable data in a way that meets NHS standards. This is done through a two-factor security approach that relies on both a password and a fluctuating key fob that cycles through the secondary authentication code. The core research team (PhD student, CI/Primary supervisor, and Co-supervisor) will be the only members with direct access to the data, which is a limit placed to ensure patient-participant confidentially across a multisite project. The Data Safe Haven also provides a secure storage method - both within the timeline of the study and in compliance with the necessary archival of the data associated with the project. Data collection through REDCap on the Data Safe Haven keeps the assurances laid out in appendix 15, as it cordons off the survey responses directly to the 1 terabyte server space set aside for the Data Safe Haven project that is registered with IT at SLMS at UCL.

All personal, identifiable data will be kept separate from the data that will be analysed in order to protect the safety and security of their identity and information. Records will be linked using a randomly generated participant identification number. Only the PhD student will have access to the dataset that has the identifiable data in order to ensure responses are linked correctly. This will allow for a de-identified dataset during the analysis process. Upon completion of the study the anonymised data will be archived on the Data Safe Haven. Personal data, without permission to contact for future research, will be stored or accessed less than 3 months after the study has ended.

Figure 4 - Flow of data from sites to Data Safe Haven

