## 16.2.2.5 In accordance with rights of data subject

Consented data will be subject to research, so all participants will be asked for consent to use their patient records as part of the informed consent process after recruitment. No data will be used without consent of the patient-participant outside recruitment.

Approaching the pseudonymisation and anonymisation as described in #5 should improve the ability to remove participant data if they revoke their consent during the study. While it may remain difficult, it is the priority of the study team to put in place security through the Data Safe Haven to allow for more participant control around the use of their data even after consent.

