## **18.1 Ethical Considerations**

The structure of the proposed research has been developed with considerations for the participants' time and emotional labour undertaken through the data collection process. Upon enrolment in the study, participant will be given details about the study, while informing them they reserve the right to leave the study and request that their information be excluded before participants are given a participant ID. Electronic consent forms will also state that they are granting permission to access patient records without concern for a change in the quality of care or need for additional prenatal health services beyond those recommended by their health care provider(s). Reliance on medical records is to ensure there is limited recall bias, and a reduction in undue stress caused to study participants by asking them to relive clinical experiences. Access to patient records will also ensure that measures will rely on prenatal tests that are taken routinely and with the expressed consent of the patient/participant, not requiring any additional consent or use of NHS resources than necessary. Utilising these sources of data removes the need for additional care or health services to be accessed for the study to be carried out.

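### Sections 11.3 and 18.1 give different cut-offs for removing a leaver's data, and 11.3 excludes all data even when a participant only wants no further surveys

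*Protocol*

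**What the plan says.** Three places in the protocol deal with data from people who leave after consenting.

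- Section 11.3 says that "they can leave the study prior to any identifiable information being removed from the dataset (also called data pseudonymisation"). It applies this to anyone who no longer wants to take part, to anyone who no longer grants access, and to anyone who wants both. In each case the person leaves "with confirmation that their data will not be included within the dataset for final analysis".
- Section 18.1 says that participants are told on enrolment that they may leave and "request that their information be excluded before participants are given a participant ID".
- Section 16.2.2.5 says that the pseudonymisation and anonymisation approach "should improve the ability to remove participant data if they revoke their consent during the study", and adds the reservation "While it may remain difficult".

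On the role of the ID, section 16 states: "Records will be linked using a randomly generated participant identification number". Section 18 likewise says that linkage is made through a randomly generated study ID. Section 16.2.2.4 places pseudonymisation, and then anonymisation, after responses have been linked, and allows identifiers to be used for linkage for up to 10 months. Section 18.2 describes direct identifiers as being removed by means of a numerical participant ID. No section says when the ID is assigned.

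**The concern.** The rule for leavers decides who is in the final analysis, so it should name one event and a consequence that fits what the participant asked for.

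On the first count, a participant who leaves after an ID exists but before pseudonymisation is excluded under 11.3 and has no right to exclusion under 18.1. If 18.1 were followed, the study would keep data, including special category data, that 11.3 promises to leave out.

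On the second count, sections 12.3.1.1 and 12.4 take birth and neonatal outcomes from routine records, not from Survey 2. Someone who wants no more questionnaires need not lose those outcomes, yet 11.3 offers only one exit, and it removes everything. Section 18.3 expects miscarriages and stillbirths in the sample. If such events make leaving more likely, the single exit removes poor outcomes more often than good ones.

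**Working it through.** The protocol gives no figure to reproduce. The check sets the passages in time order.

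**Step 1: order of events.** Section 16 uses the participant ID to link records, and section 18 repeats this. On that text the ID exists by the time of linkage. Section 16.2.2.4 puts pseudonymisation after linkage and anonymisation after that. Section 16.3.6 deletes the key once data are anonymised, except for people who agreed to future contact. The order is ID, linkage, pseudonymisation, anonymisation with key deletion.

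**Step 2: the same withdrawal under each section.**

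| Time of withdrawal | 11.3 | 18.1 |
|---|---|---|
| Before the ID | excluded | excluded on request |
| After the ID, before pseudonymisation | excluded | no right to exclusion |
| After pseudonymisation | no right to exclusion | no right to exclusion |

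The conflict is in the middle row.

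**Step 3: length of the middle row.** This depends on when the ID is assigned, which is not stated.
- If it is assigned at enrolment (an assumption), the window could last up to about 10 months per participant, the maximum in 16.2.2.4.
- If it is assigned only at pseudonymisation (one reading of 18.2), the window is zero.

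**Step 4: the consequence of leaving.** Section 11.3 joins stopping participation and withdrawing access with an and/or and gives both one result. There are four possible data sources per participant: Survey 1, Survey 2, the parent's record and the infant's record. A person who asks only to be spared Survey 2 loses all four under 11.3, although only one is at issue.

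**Step 5: size.** Let *w* be the share who leave and are excluded, *a* the adverse-outcome rate in those who stay, and *b* the rate in those who leave. The rate in all participants is (1 − *w*)*a* + *wb*. The rate after exclusion is *a*. The difference is *w*(*b* − *a*), which is zero if leaving is unrelated to outcome. The protocol gives none of *w*, *a* or *b*. For scale only, each 1% excluded is 0.01 × 800 = 8 participants in the full sample, or 0.01 × 200 = 2 in the LGBTQIA+ group.

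**The case against.** The strongest reply is that ID assignment may itself be pseudonymisation. Section 16.2.2.4 names direct identifiers such as name and hospital ID as the means of linking accounts, and section 16.2 lists identifiers for the same purpose. The glossary describes pseudonymisation as a process that may replace names with something else, and 18.2 says that identifiers are removed by means of the ID. Read that way, 11.3 and 18.1 name one event in two forms of words. The flowchart that 16.2.2.4 relies on is not visible in the text reviewed, so the order cannot be settled from it.

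This reading is possible, but it is not the more natural one. Sections 16 and 18 tie the ID to linkage, and 18.2 itself says that the case labels and key prevent duplicate cases during data collection, which implies that IDs are in use before the end. The objection turns a certain contradiction into a probable one; it does not remove the need to reconcile the sections.

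Three stronger readings are tempting, and the documents do not support them.

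- A reader might infer a third cut-off, any time during the study, from 16.2.2.5. That section states a hedged ability, not a promise. The statement in section 18 that people may withdraw at any time concerns participation and is silent on data already held.
- A reader might infer that everyone who does not complete Survey 2 is erased. Section 11.3 concerns people who choose to leave. It does not cover those who simply do not respond.
- A reader might put a figure on the bias. Any withdrawal rate or excess risk in leavers would be invented, and the expression in step 5 concerns a crude rate, whereas section 14.1 plans a longitudinal structural equation model compared between groups.

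It can also be said that the participant information sheet and consent form, which are not shown, may already separate the two ways of leaving. If so, 11.3 still needs to match them.

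**Conclusion.** The point holds in two parts. First, 11.3 and 18.1 state different cut-offs for excluding a leaver's data, and on the more natural reading of sections 16, 16.2.2.4 and 18 these are different moments. Because 18.2 permits a reading in which they coincide, the finding is that the passages must be reconciled, not that two incompatible rules are proven. Section 16.2.2.5 should be brought into line but is not a rule of its own.

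Second, 11.3 attaches exclusion of all data to any choice to leave, so a participant who leaves only to avoid further surveys also loses Survey 1 and record-based outcomes they had agreed to. This part does not depend on when the ID is assigned. Whether it biases the results depends on leaving being related to outcome, which is plausible after a poor birth outcome or a loss but is not shown. The number affected and the effect on the planned model cannot be derived. This is a worthwhile, inexpensive improvement, not a demonstrated distortion of the results.

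**What to change.** - State one cut-off event, in the same words, in 11.3 and 18.1. Say when the participant ID is assigned relative to enrolment, linkage and pseudonymisation.
- Align 16.2.2.5 with that cut-off, and check the participant information sheet and consent form against it.
- Replace the single exit in 11.3 with two: (a) no further surveys or contact, with data already given and the consented record linkage for parent and infant kept in the analysis; (b) withdrawal of consent, with all data removed up to the cut-off.
- Report the number choosing each option, separately for LGBTQIA+ and cisgender heterosexual participants.

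The cost is a wording amendment to the protocol and, where they differ, to the participant documents. Option (a) may be a new choice for participants, so the information sheet and consent form would have to describe it. No additional type of data is collected.
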